This academic, mono center, randomized, double blind, double dummy, placebo controlled, parallel-group study will be carried out in the Department of Oto-rino-laryngology of the University Hospitals Leuven in 2014, and be running until March 2018.

The following milestones will be outlined:

- August 2014: Preparation of the logistics of the clinical trial.
- September 2014: EudraCT number application and submission at CTC and MEC of the University Hospitals Leuven, without major expected problems in the light of the previous proof-of-concept study and reputation of the research team of [name]. [name].
- January 2015: First IR patient included in this trial.
- July 2015: Last visit of first included patient.
- October 2017: Last IR patient included in this trial.
- April 2018: Last visit of last included patient, all ELISAs performed, and start of data analysis.

[figure not shown]

Table 1: Visualization of the time management of the study

Involved investigators:

- Apr. [name] fellow (screening and clinical follow-up) ([contact])
- CTA [name]
- [name] fellow
- [name] [name] fellow
- CTA [name]
- [name] [name] (recruitment, screening and clinical follow-up)
- [name]. [name] (recruitment and screening and principal investigator)

B. Inclusion criteria

The following criteria will be administered for the screening of a patient in order to obtain inclusion of the patient in our study:

- IR patients with at least 2 persistent (> 12w) rhinological symptoms (nasal discharge, sneezing, nasal congestion) for an average of at least 1 h per day,
- IR patients with a total nasal symptoms score (TNS) of 5 or more on a visual analogue scale (VAS).
- Age > 18 and < 60 years.
- Written informed consent.
- Willingness to adhere to visit schedules.
- Adequate contraceptive precautions in female patients with childbearing potential. **

C. Exclusion criteria

Patients meeting the following criteria will be excluded out of the study:

- Patients with concomitant allergic rhinitis, demonstrated by positive skin prick test (Hal reagents) and/or IgE in blood. *
- Patients with structural abnormalities: nasal polyps, severe septal deviation (septum reaching concha inferior or lateral nasal wall), septal perforation, hypertrophy of the inferior turbinates.
- Patients with local allergic rhinitis (LAR) or entopy.

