- Systemic steroid treatment less than 4 weeks before the inclusion in the study, nasal steroid spray less than 4 weeks before the inclusion, oral leukotriene antagonists or long-acting antihistamines less than 2 weeks before the inclusion.
- Inability of the patient to stop taking medication affecting nasal function like β -blockers.
- History of prolonged use or abuse of decongestant nasal spray like xylometazoline spray and/or use or abuse of decongestive oral medication.
- Evidence of infectious rhinitis/rhinosinusitis or common cold within 4 weeks prior to inclusion.

- Pregnancy or lactation. **
- Any disorder of which might compromise the ability of a patient to give truly informed consent for participation in this study.
- Enrollment in other investigational drug trial(s) or receiving other investigational agent(s) for any other medical condition.
- Contra-indications for the use of local anesthesia (cocaine 5%).
- Smoking or occupational exposure to irritants (like hypochlorite, persulfates, isocyanates).
- Nasal malignancies or severe comorbidity like granulomatosis or vasculitis.

*Note *:*

Patients with underlying allergic disease are defined by positive skin prick test for the 18 most prevalent inhalant allergens (house dust mite, timothy grass, smooth meadow grass, orchard grass, nettle, plantago, oxeye daisy, mugwort, alder, birch, hazel, horse, cat, dog, rabbit, Alternaria, Aspergillus and Cladosporium - HAL Allergy, Leiden, The Netherlands) and/or positive IgE analysis in the blood.

*Note **:*

Female patients with childbearing potential will be offered a pregnancy test at the screening.

D. Possible hurdles

Based on the former studies in which the therapeutic effect of capsaicin is proven (9) (10) (11) (12) (13) (18) and given the fact that capsaicin is well tolerated and side effects are minimal, it is very unlikely to be subject of foreseen or unforeseen obstacles in the elaboration of this study protocol. Beside minor inconveniences such as rhinorrhea, sneezing and watery eyes, there are no other known side effects.

With regard to the safety of all individuals, the study will immediately be abrogated and the treatment protocol we will un-blinded at once, in case of any allergic reaction or any other adverse event.

Methodology

A. Study onset

This study will include 4 parallel arms of equal sample size.

120 IR patients will be included in this four-arm study (n=30 patients per treatment arm).

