- An announcement at the University website will be placed, explaining the aims and a short study protocol.
- An announcement 'ad valvas' in the University Hospitals of Leuven will be placed, explaining the aims and a short study protocol.
- ENT doctors will be contacted in order to provide them the possibility to offer their IR patients without AR with at least one nasal symptoms (rhinorrhea, nasal blockage, nasal itching and/or sneezing (1)) and/or NHR symptoms induced upon encounter of certain stimuli (humidity changes, temperature changes, smoke other scents, physical activity and emotional stress (5)) with capsaicin nasal spray.
- An advertisement will be placed in local newspapers such as Metro, Randkrant, ...

Prior to any study-related measure, patients will be informed both verbally and in writing about the aim and nature of the study, the anticipated benefits and risks, the discomfort to which they may be exposed, and also about their right to withdraw from participation in the study at any time after their own free will. After given informed consent, patients will be offered a screening visit with [name]. [name], [name] [name] at week -3. CTA [name] and Apr. [name] will plan all visits.

All eligible patients will be invited to return after three weeks for randomization and start of the study.

Patients will receive a financial compensation for transportation and participation in agreement with the current standards of the local Medical Ethical Committee of the University Hospitals of Leuven (see Informed Consent Form).

F. Randomization

[name] will provide a randomization list.

• ² G. Molenberghs and G. Verbeke (2005). Models for discrete longitudinal data, Springer-Verlag, New-York

For tracking purposes and for double-blinded randomization, all patients will be allocated a study number starting with Caps001 until Caps120.

Patients will be allocated on a one to one base to receive either capsaicin nasal spray or placebo.

For each patient, an envelope with the study code will be kept in a locker at the office of the CTA [name] ([name]) of the Outpatient clinic of the Department of Otorhinolaryngology, [name], in case of urgent need to un-blind the study in case of any adverse event.

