As this study will include four parallel arms of equal sample size, the 120 included IR patients will be randomized in four equal groups of each 30 patients (n=30 patients per treatment arm). A block randomization with varying block sizes will be used.

G. Demographic and clinical information

Patient's demographic information as well as general medical history will be gathered from medical records and verified during the screening visit to the Outpatient clinic.

Demographic data of importance are: age, gender, smoking, occupation, exposure to agents during professional or recreational activity, concomitant bronchial disease (asthma, COPD), aspirin intolerance and current medication use.

The respective information is gathered in case report forms (CRFs) and will be analyzed by GraphPad Prism 6.

H. Time schedule and visit table

[figure not shown]

Table 2: Schematic visualization of the timeframe and visit table

As demonstrated in table 1, the included patients will visit the ENT Department of UZ Leuven at six occasions.

- Screening visit (week -3)

Explanation of study, study protocol and treatment.

Inclusion in study after signing the informed consent form.

Evaluation of inclusion and exclusion criteria.

Pregnancy test for women with childbearing potential.

Skin prick test for common aero-allergens if not yet performed.

Blood tests for total and/or specific IgE.

Nasal endoscopy for exclusion of anatomic deformities, rhinosinusitis or nasal polyps.

Symptom evaluation using VAS scores for individual and total nasal symptoms.

Quality of life evaluation using the rhinitis quality of life questionnaire (RQLQ).

- Baseline visit (week -1):

Re-evaluation of the inclusion and exclusion criteria.

Clinical nasal examination including nasal endoscopy.

NHR challenge (by CDA provocation and/or hyperosmolar discs).

Nasal fluid collection before and after NHR challenge.

Evaluation of nasal airflow by peak nasal inspiratory flow (PNIF) device before and after NHR provocation.

Symptom evaluation using VAS scores for individual and total nasal symptoms.

Quality of life evaluation using the rhinitis quality of life questionnaire (RQLQ).

- Randomization and start of treatment (week 0):

Explanation treatment i.e. five applications of capsaicin/placebo nasal spray with a one-hour interval, followed by handing over the capsaicin nasal spray or placebo for the following four weeks.

Brief nasal examination.

Evaluation of adverse events.

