Two weeks after treatment, patients will be contacted by telephone in order to evaluate adverse events, check adherence and evaluate therapeutic response.

- Follow-up visit 1 (week 4):

Nasal examination including nasal endoscopy.

NHR measurements by CDA and/or hyperosmolar discs.

Nasal fluid collection by Merocell (both nostrils) for measurement of neuromediators before and after NHR measurements.

Measurement of PNIF before and after NHR measurements.

Evaluation of the therapeutic response (TRE) on a scale from 1 (= no relief of symptoms) to 5 (= total relief of symptoms).

Symptom evaluation (VAS) for INS and TNS.

Quality of life evaluation using the RQLQ.

Evaluation of adverse events and check of adherence.

- Follow-up visit 2 (week 12):

Identical to FU 1

- Follow-up visit 3 (week 26):

Nasal examination including nasal endoscopy.

Evaluation of the therapeutic response (TRE) on a scale from 1 (= no relief of symptoms) to 5 (= total relief of symptoms).

Symptom evaluation (VAS) for INS and TNS.

Quality of life evaluation using the RQLQ.

Evaluation of adverse events and check of adherence.

	Screening week -3	Baseline week -1	Treatment week 0	FU visit 1 week 4	FU visit 2 week 12	FU visit 3 week 26
Explanation study and protocol	x					
Informed consent	x					
Evaluation in-and exclusion criteria	x	x				
Pregnancy test (if necessary)	x					
SPT (if necessary)	x					
Blood analysis	x					
ENT exam with nasal endoscopy	x	x	x	x	x	x
Nasal fluid collection		x/x*		x/x*	x/x*	
Explanation R/	x		x			
Start R/, handing over study medication and diary			x			
NHR measurements		x		x	x	
TRE				x	x	x
Symptom evaluation VAS	x	x		x	x	x
Symptom evaluation RQLQ	x	x		x	x	x
AEE and check adherence			x	x	x	x

ENT: ear, nose, throat

TRE: therapeutic Response Evaluation

AEE: Adverse Events Evaluation

*: x/x = before and after NHR measurements

Table 3: Overview of registrations and sample collections that were performed at each visit

I. Variables

- Clinical ENT exam:

Nasal endoscopy will be performed by an experienced MD.

- Skin Prick Test (SPT):

SPT for the 18 most prevalent inhalant allergens (e.g. house dust mite, grass, mugwort, alder, birch, hazel, pet animals, Alternaria, Aspergillus) provided by HAL Allergy, will be performed by investigators Apr. [name] or CTA [name].

- Blood analysis:

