On the day of the treatment, all IR patients will be treated by [name]. [name], [name] [name], Apr. [name] or CTA [name] with a blinded nasal spray (capsaicin or placebo) five times with one-hour intervals as described by the treatment protocol of Van Rijswijk et al. (13). The nasal mucosa of all patients will be anaesthetized prior to the first three applications by 2 puffs of cocaine 5% nasal spray in each nostril. To ensure effective local anesthesia, an interval of 10 to 15 minutes was maintained.

To protect the eyes of the patients against potential irritating particles of capsaicin, all individuals will be suggested to close their eyes during the application of capsaicin nasal spray.

After finalizing the treatment protocol, the patient will be handed over a nasal spray containing capsaicin 0,01mM, capsaicin 0,001mM or placebo to take home and to use for the consecutive four weeks, labeled with his/her allocated study number (Caps001-Caps120) and the usage (2 puffs in each nasal cavity once daily).

- Evaluation of nasal symptoms by VAS scores:

All patients will be asked to mark the typical nasal symptoms on a visual analogue scale for individual (INS) and total nasal symptoms (TNS) before treatment and at week 4, 12 and 26. A visual analogue scale is a measurement of a patient's subjective evaluation of symptom severity by indicating a position on a line between two endpoints, which represent a well-validated and easy technique of the evaluation of symptom severity. Indeed, VAS scores for TNS have recently been validated and proposed as a means of evaluation of symptom control in rhinitis (20).

- Evaluation of quality of life by Rhinitis Quality of Life Questionnaire:

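### The only pregnancy test is offered 21 days before first dosing, with no required negative result and no repeat at week 0

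*Combined protocol and SAP*

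**What the plan says.** Under Study design, B. Inclusion criteria, the plan requires "Adequate contraceptive precautions in female patients with childbearing potential". Section C, Exclusion criteria, rules out pregnancy and lactation. Both entries point to the double-asterisk note at the end of section C: "Female patients with childbearing potential will be offered a pregnancy test at the screening".

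The test appears in two further places, both under Methodology, H. Time schedule and visit table:

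- The screening visit (week -3) lists "Pregnancy test for women with childbearing potential" as an ordinary procedure.
- Table 3 has one mark in its pregnancy-test row, in the screening column. The row label adds that the test is done if necessary, which most naturally means if the patient is of childbearing potential.

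The baseline visit (week -1) includes "Re-evaluation of the inclusion and exclusion criteria" but lists no pregnancy test. The week-0 visit lists explanation of treatment, a brief nasal examination and adverse events.

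On timing, Methodology, E. Patient recruitment states: "All eligible patients will be invited to return after three weeks for randomization and start of the study". On exposure, Methodology, I. Variables (Product application) states: "The nasal mucosa of all patients will be anaesthetized prior to the first three applications by 2 puffs of cocaine 5% nasal spray". Study spray follows on the same day, and then four weeks of spray at home.

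**The concern.** The plan means to keep pregnant women out of the trial but does not confirm that they are out when exposure begins. There are two separate gaps.

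1. **Status of the test.** It is described as an offer. No text we could read says that a negative result is a condition of randomisation, or what happens if a woman declines. By contrast, the single-asterisk note in the same section ties the allergy exclusion to skin prick and IgE results.
2. **Timing of the test.** It comes three weeks before first dosing and is not repeated.

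At stake is participant safety and the integrity of an eligibility criterion. Every arm receives cocaine 5% at week 0, so allocation to placebo does not avoid exposure. No estimate, sample size, alpha or power depends on this.

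**Working it through.** The plan gives no figure to reproduce. The check sets the visit entries side by side, then does simple date arithmetic and a bounding calculation.

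**Entries by visit (section H list and Table 3)**

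| Visit | Pregnancy test | Criteria check | Cocaine 5% and study spray |
|---|---|---|---|
| Week -3 | Yes | Yes | No |
| Week -1 | No | Yes | No |
| Week 0 | No | No | Yes, all arms |

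The visit list and Table 3 agree on the timing of the test.

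**Intervals**

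- Test to first dosing: 3 × 7 = 21 days.
- Last criteria check (week -1, no test) to first dosing: 7 days.
- Test to the end of the home spray (week 4): 21 + 28 = 49 days.

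**What a week-0 test adds.** Any test misses conceptions within some detection lag of L days.

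- A week -3 test can detect conceptions up to day -21 - L.
- A week-0 test can detect conceptions up to day -L.
- The difference is 21 days of conceptions, whatever L is.

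**Expected number.** With n women of childbearing potential and a pregnancy rate r per woman-year, the expected additional pregnancies within reach of a week-0 test are n × r × 21/365. The documents give neither n nor r. We assume n from 30 to 60 of the 120 patients, and r from 1% to 10% per woman-year despite reported contraception.

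- Low: 30 × 0.01 × 21/365 = 0.017.
- Middle (n = 45, r = 3%): 45 × 0.03 × 21/365 = 0.08.
- High: 60 × 0.10 × 21/365 = 0.345.

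Under these assumptions each result is an upper bound for the timing gap, because some pregnancies would be recognised and reported before dosing. None of them covers the first gap: a woman already pregnant at week -3 who declines the offer is not counted, and the documents give no rate for that.

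**The case against.** The strongest reply is that the plan already has several safeguards and the residual risk is very small.

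- **The word offered may be loose drafting.** The screening list names the test as a plain procedure, and Table 3 is compatible with a routine test in women of childbearing potential. Anyone who tests positive is excluded in any case. This is fair, and a required test may well be intended. But the text does not say so, and it leaves open what happens when the offer is declined.
- **Other checks exist.** Contraception is required, criteria are re-evaluated seven days before dosing, and contra-indications to cocaine 5% are a separate exclusion. These lower the risk. They work by enquiry, however, so none would find a pregnancy the woman does not know about.
- **The yield is low and rests on assumptions.** This stands. The upper figure needs both inputs at their maximum in a population selected for contraception. The case for change cannot rest on frequency.
- **No harm is quantified.** This also stands. The documents say nothing about fetal risk from one day of topical cocaine or from dilute capsaicin. They show only that pregnancy was judged a reason to exclude.
- **Not everything could be read.** The consent form and Table 2 were not available to us, and pregnancy instructions may appear in the consent form. That limits the point about a required result more than the point about timing, on which the visit list and Table 3 agree.

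**Conclusion.** The concern holds. As written, the plan could dose a woman it intends to exclude, either because she declined an offered test or because a test 21 days earlier could not have detected the pregnancy. The 21-day gap follows directly from the schedule and needs no assumption. The expected yield of closing it, at most about 0.02 to 0.35 pregnancies in the trial, depends entirely on the assumed number of women and the assumed pregnancy rate. This is an improvement the sponsor should make because it costs almost nothing, not because the event is likely. It is a safety and eligibility point with no statistical consequence.

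**What to change.** - Reword the double-asterisk note so that women of childbearing potential must have a negative pregnancy test at screening and again at week 0.
- State that the week-0 result must be available before randomisation and before the first anaesthetic puff.
- Add the test to the week-0 visit list and to the week-0 column of Table 3.

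The cost is one inexpensive repeat test per woman of childbearing potential and three small text changes. Patients already spend hours on site that day for five applications at one-hour intervals, so a quick test adds little burden.

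If only one test can be done, it should be the week-0 one. Repeating is still better than moving, because otherwise an occasional pregnant patient would go through medication washout and the week -1 cold dry air challenge before being found ineligible. A week-0 test will still miss the very earliest conceptions and any that occur during the four weeks of home spray.

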- To evaluate if two novel treatment modalities (explained more briefly on page 9 in paragraph 'Study Onset' of chapter 'Methodology') show non-inferiority on subjective evaluations (symptom score on a Visual Analogue Scale (VAS), Therapeutic Response Evaluation (TRE) and Rhinitis Quality of Life Questionnaire (RQLQ)) compared to the current treatment modality of capsaicin nasal treatment in patients with IR. The gathered data of this single center trial can be used to guide the decision on the set-up and the design of a larger multi-center trial being powered to prove non-inferiority.

Our secondary aims are:

- To evaluate if the two novel treatment modalities show non-inferiority compared to the current treatment modality of capsaicin nasal treatment in patients with IR on objective evaluations (Peak Nasal Inspiratory Flow (PNIF) measurements before and after CDA challenge).
- To evaluate the occurrence of adverse events at week 4, week 12 and week 26 and recurrence of symptoms and NHR at week 26 in the different treatment groups.

B. Hypothesis

Non-inferiority in efficacy of the two novel treatment regimes i.e. capsaicin nasal spray 0,01mM (2puffs/nostril/day) during 4 weeks and capsaicin nasal spray 0,001mM (2puffs/nostril/day) during 4 weeks compared to the current treatment of capsaicin nasal spray 0,1mM (5/day administered on a single day) with regard to the scores on week 4 (taking into account the baseline level).

C. Outcome

- VAS for major nasal symptom at week 4, week 12 and week 26. The region of equivalence is defined as a difference in VAS of less than 1.
- VAS for total and individual nasal symptoms at week 4, week 12 and week 26. The region of equivalence is defined as a difference in VAS of less than 1.
- TRE (based on a scale from 1 to 5) at week 4, week 12 and week 26. The region of equivalence is defined as a difference in percentage for patients of less than 10% in all different TRE scoring groups.

- NHR (objectively measured by PNIF before and after CDA challenge) in all treatment modalities at week 4, week 12 and week 26. The region of equivalence is defined as a drop in PNIF of less than 10%.
- Appearance of adverse events at week 4, week 12 and week 26.
- Recurrence of symptoms (based on a scale of 1 to 5) at week 26.

Study design

A. Type of study

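### The written safety rule stops and un-blinds the whole study for any adverse event, which contradicts the plan's own dropout and recruitment provisions

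*Combined protocol and SAP*

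**What the plan says.** **The rule.** The last paragraph of Study design, D. Possible hurdles reads: "With regard to the safety of all individuals, the study will immediately be abrogated". The same sentence goes on to un-blinding and names the trigger: "immediately be abrogated and the treatment protocol we will un-blinded at once, in case of any allergic reaction or any other adverse event". Just before it, the section says of capsaicin: "Beside minor inconveniences such as rhinorrhea, sneezing and watery eyes, there are no other known side effects". It does not say whether these reactions count as adverse events for the rule.

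**Aims.** Under Objectives, A. Aims, the primary aim asks whether the two new regimens "show non-inferiority on subjective evaluations", namely VAS, TRE and RQLQ. One secondary aim concerns "adverse events at week 4, week 12 and week 26 and recurrence of symptoms and NHR at week 26 in the different treatment groups".

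**Dropout and recruitment.** Methodology, C. Sample size and setting allows for 10% dropout and gives unrelated adverse events as one of three causes. If 120 patients have not been included after three years, recruitment goes on until they have.

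**Code breaking.** Methodology, F. Randomization keeps one code envelope per patient for urgent need. It describes the purpose as un-blinding the study, and the occasion as any adverse event.

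**Anaesthetic.** Under Methodology, I. Variables (Product application), every patient receives cocaine 5% nasal spray before the first three applications, whatever the arm.

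**The concern.** The rule names the study, not the patient, as the thing to be stopped, and any adverse event as the trigger. Taken at its word, a single mild or unrelated event in one of 120 patients ends the trial and opens the allocation. So does a reaction to the anaesthetic in a placebo patient. Patients still in follow-up would then not complete the evaluation to week 26. The arms would fall short of 30 if the event came before the last inclusion.

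The more likely course is that staff do not follow the sentence. They would then be departing from a written safety rule. In its place they would have only the envelope provision, whose one criterion, urgent need, is undefined and tied again to any adverse event. Nothing visible says which events stop one patient's treatment and which should halt the study. Needless code breaks matter here because the primary aim rests on patient-reported scores, which knowledge of treatment can influence.

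**Working it through.** **1. The plan's own figures.** Four arms of 30 give 4 × 30 = 120. Dropout of 10% is 0.10 × 120 = 12 patients, leaving 108. Both follow from Methodology, A and C. The 120 is a feasibility number, so there is no power calculation to reproduce.

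**2. The provisions side by side.** This step needs no event rate.

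| Section | Consequence of an adverse event | Level |
|---|---|---|
| Study design, D | Study stopped and un-blinded | Study |
| Methodology, C | An unrelated event may cause dropout; recruitment continues to 120 | Patient |
| Methodology, F | That patient's envelope is available in urgent need, but the wording speaks of un-blinding the study for any event | Mixed |
| Objectives, A | Events are evaluated by group at weeks 4, 12 and 26 | Needs follow-up to continue |

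The first two rows cannot both hold. If even one of the 12 allowed dropouts came from an unrelated adverse event, the rule in the first row would already have closed the study. The third row leans towards patient-level action without saying so. The fourth is not a contradiction in itself, but the evaluation would be cut short if the rule fired early.

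**3. How often the literal rule would fire (illustration only).** Let r be the chance that a patient has at least one adverse event over 26 weeks. The documents give no value, so r is assumed, taken as equal and independent across patients, with dropout ignored.

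P(at least one event among 120) = 1 − (1 − r)^120

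| Assumed r | (1 − r)^120 | P(rule fires before all 120 finish) |
|---|---|---|
| 0.1% | 0.887 | 0.113 (11%) |
| 1% | 0.299 | 0.701 (70%) |
| 5% | 0.0021 | 0.998 (99.8%) |

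The even-odds point is r = 1 − 0.5^(1/120) = 0.0058, or about 0.58%. If the expected local reactions count as adverse events, rates at the low end of the table are hard to credit. If they do not count, the rate is simply unknown.

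**The case against.** The strongest defence is that the protocol, read as a whole, makes the intention plain. The sentence is visibly garbled and closes a section on possible hurdles. The operational sections keep one envelope per patient, treat unrelated events as dropout, and collect adverse events at visits, by telephone and by diary. A sensible investigator would break one code and carry on. One envelope exposes one patient in 120, and varying block sizes limit what it reveals about others.

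Much of this stands. It supports calling the sentence a drafting error, and it rules out several stronger readings that a reader might infer:

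- **That the trial is likely to be stopped early.** The documents give no adverse event rate, and the envelopes suggest that staff would act on individual patients. The probabilities describe only the literal rule under assumed rates.
- **That listing adverse events as an aim contradicts having a stopping rule.** It does not; trials routinely have both. The real conflict is with the dropout and recruitment text.
- **That there is no criterion at all for opening an envelope.** Urgent need is a criterion, though a vague one.
- **That un-blinding would bias the results by some known amount.** Nothing in the documents allows this to be sized.

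What does not stand is the conclusion that nothing need change. The envelope text repeats both the study-level object and the unlimited trigger, so it cannot be relied on to correct the rule. That the documents do not settle the matter can be said only of the visible text; the diary addendum, for example, is not shown.

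**Conclusion.** The rule is wrong as written and should be fixed. It contradicts Methodology, C. Sample size and setting, and Methodology, F. Randomization points towards patient-level code breaks without settling the matter. This conclusion rests on the wording alone and needs no assumed rate.

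Its practical size cannot be fixed from the documents. Under the literal reading, the chance of firing before 120 patients finish runs from 11% to 99.8% as the assumed per-patient rate goes from 0.1% to 5%. That range shows only that the rule is unworkable unless adverse events are very rare. It does not forecast what would happen in this trial.

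**What to change.** Reword the sentence in Study design, D. Possible hurdles, and align the envelope sentence in Methodology, F. Randomization, so that:

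- **Treatment:** an adverse event leads, where clinically needed, to stopping treatment for that patient only.
- **Code break:** only that patient's envelope is opened, and only when knowing the treatment is needed for urgent care. Each code break is logged.
- **Expected local reactions:** rhinorrhea, sneezing and watery eyes are recorded as adverse events and do not by themselves stop or un-blind the study.
- **Whole-study pause:** this is kept for a stated serious trigger chosen by the investigators and the ethics committee, for example a related serious adverse event or a severe allergic reaction.

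The first two items follow from what sections C and F already imply. The last two are reasonable defaults that the documents do not dictate, and they relax a conservative rule, so the investigators and the ethics committee should set them.

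**Cost.** A short amendment and a code-break log. The milestones in Study design, A. Type of study list "EudraCT number application and submission at CTC and MEC of the University Hospitals Leuven", so replacing a written safety rule needs ethics review. The new text also relies on investigators judging severity and relatedness while blinded. It adds no visits or patients, and the analysis does not change.
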